5.0 OBJECTIVES

The primary objective is to evaluate the efficacy, as measured by improvement in MADRS total score, at 1 day after the initial single oral dose of AGN-241751 compared with placebo in participants with MDD. The key secondary objectives are to evaluate the efficacy at Day 8, Day 9 after single oral dose, at Day 15 after repeated dose, and at Day 22, 7 days after the completion of AGN-241751 dosing, when administered orally once daily compared with placebo in participants with MDD.

6.0 PARTICPANT POPULATIONS

6.1 MODIFIED INTENT-TO-TREAT POPULATION

The modified intent to treat (mITT) population includes all randomized participants who received at least 1 administration of study treatment and have a baseline MADRS total score and at least 1 postbaseline assessment for the MADRS total score during the double-blind treatment period. Participants will be summarized according to the randomized study treatment.

6.2 SAFETY POPULATION

The safety population includes all participants who received at least 1 administration of study treatment. Participants will be summarized according to the study treatment they actually received.

7.0 PARTICIPANT DISPOSITION

The number and percentage of participants in 2 of the study populations (Safety and mITT) will be summarized by treatment group and study center; the number of participants screened will be summarized overall only by study center.

Screen-failure participants (i.e., participants screened but not randomized) and the associated reasons for failure to randomize will be tabulated overall for the all screened participants. The number and percentage of participants who enter the double-blind treatment period, complete the double-blind treatment period and of participants who prematurely discontinue during the same period will be presented for each treatment group and pooled across treatment groups. The reasons for premature discontinuation from the double-blind treatment period as recorded on the termination pages of the electronic case report forms will be summarized (number and percentage) by treatment group. Similar disposition information to the double-blind treatment period will be presented for the safety follow-up period. The end of the study is defined as the completion of enrollment and completion of all periods of the study. All participants who prematurely discontinue during the double-blind treatment period or the safety follow-up period will be listed by discontinuation reason.

8.0 DEMOGRAPHICS AND OTHER BASELINE CHARACTERISTICS

Demographic parameters (age; age group (<20, 20-29, 30-39, 40-49, 50-59, and >=60); race; ethnicity; sex), baseline characteristics (weight; height; and body mass index, calculated as weight [kg]/(height [m])² will be summarized descriptively by treatment group for the Safety and mITT populations. Continuous variables will be summarized by number of participants and mean, SD, median, Q1 (25 percentile), Q3 (75 percentile), minimum, and maximum values. Categorical variables will be summarized by number and percentage of participants.

Abnormalities in participants' medical and surgical histories will be coded using the *Medical Dictionary for Regulatory Activities* (MedDRA), version 22.0. The number and percentage of participants with abnormalities in medical and surgical histories in each system organ class and preferred term will be summarized by treatment group for the Safety Population.

Prior medication is defined as any medication taken before the date of the first dose of study treatment. *Concomitant medication* is defined as any medication taken on or after the date of the first dose of study treatment.

Both prior and concomitant medications will be coded by drug name and therapeutic class. The use of prior and concomitant medications will be summarized by the number and percentage of participants in each treatment group for the Safety Population. If a participant took a specific medication multiple times or took multiple medications within a specific therapeutic class, that participant would be counted only once for the coded drug name or therapeutic class.

Formulations (including salts, esters, etc) containing the same active ingredient will be pooled under the coded drug name of the base compound. Medications containing multiple active ingredients of different coded drug names will be reviewed during the course of the study and may be pooled under a single coded drug name for analyses.

The number and percentage of participants taking each antidepressant therapy (ADT) and the number of ADTs (0, 1, 2, and >2) received in current episodes of major depressive disorder prior to randomization will be summarized by treatment group for the Safety Population. ADT medication selection criteria is included in [Table 8-1](#).

Table 8-1 Criteria for ADT medication

ADT Class	Medication List
Atypical	BUPROPION
	MIRTAZAPINE
	VILAZODONE and/or VILAZODONE HYDROCHLORIDE
	VORTIOXETINE and/or VORTIOXETINE HYDROBROMIDE
SNRI	DESVENLAFAXINE and/or DESVENLAFAXINE SUCCINATE
	DULOXETINE and/or DULOXETINE HYDROCHLORIDE
	LEVOMILNACIPRAN and/or LEVOMILNACIPRAN HYDROCHLORIDE
	VENLAFAXINE and/or VENLAFAXINE HYDROCHLORIDE
SSRI	CITALOPRAM and/or CITALOPRAM HYDROBROMIDE
	ESCITALOPRAM and/or ESCITALOPRAM OXALATE
	FLUVOXAMINE
	FLUOXETINE and/or FLUOXETINE HYDROCHLORIDE
	PAROXETINE and/or PAROXETINE HYDROCHLORIDE
	SERTRALINE

World Health Organization (WHO) Drug Dictionary, March 2017, will be used to classify prior and concomitant medications by therapeutic class and drug name.

Data for medical history with onset dates prior to the Screening visit will be tabulated and presented using the Safety population. An overall total will be provided for the study as well as by treatment group. Medical history data will be coded using the MedDRA version 22.0 dictionary. No statistical comparisons will be performed.

A significant protocol deviations listing will be provided for protocol deviations for the Randomized Participants. Protocol deviations will be defined in a separate document, including importance classification.

9.0 EXTENT OF EXPOSURE AND TREATMENT COMPLIANCE

9.1 EXTENT OF EXPOSURE

Exposure to the study treatment for the Safety Population during the double-blind treatment period will be summarized by treatment group (placebo, 3mg, 10mg and 25mg). Descriptive statistics (number of participants, mean, SD, median, Q1 (25 percentile), Q3 (75 percentile), minimum, and maximum) will be presented for each study day from Day 1 to Day 15.

The following parameters for the study treatment will also be summarized using descriptive statistics by treatment group:

- Treatment duration overall and by treatment regimen intervals (Day 1, Day 2-Day 7, Day 8-Day 15). Treatment duration will be calculated as the number of days from the date of the first dose of study treatment to the date of the last dose of study treatment, inclusive.

9.2 MEASUREMENT OF TREATMENT COMPLIANCE

Dosing compliance for the double-blind treatment period is defined as the number of tablets actually taken by a participant during that period divided by the number of days the participants are expected to be taken during the same period multiplied by 100. If a participant achieved 80 to 120 percent compliance, then participant is considered as a compliant. Descriptive statistics (number and percentage) will be used to summarize compliant rates.

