7.1. Treatments Administered

7.1.1. Part A

On Day 1, site staff will give the participant the single dose of double-blind study treatment from Bottle 1 (for applicable visit) to take by oral ingestion in the clinic (ie, the first dose of study treatment for that week). Site staff will then give Bottle 2 (for applicable visits), which contains the single-blind placebo tablets, to the participant with the instruction to take 1 tablet daily by oral ingestion for the remainder of that week (Days 2 through 7). On Day 8, site staff will give the participant the single dose of double-blind study treatment from Bottle 1 (for applicable visit) to take by oral ingestion in the clinic (ie, the first dose of study treatment for that week). Site staff will then give Bottle 2 (for applicable visits), which contains double-blind study treatment, to the participant with the instruction to take 1 tablet daily by oral ingestion for the remainder of that week (Days 9 through 15).

Study Treatment Name	AGN-241751	Placebo
Dosage Formulation	Tablet	Tablet
Unit Dose Strengths	3 mg 10 mg 25 mg	-
Route of Administration	Oral	Oral
Dosing Instructions (Part A)	
At Day 1, the first dose from Bottle 1 (for applicable visit) given by site staff to the participant for oral ingestion in the clinic; Bottle 2 (for applicable visits) will be given to participant to take home with instructions to take 1 tablet orally every day for the rest of the week.
 
At Day 8, the first dose from Bottle 1 (for applicable visit) given by site staff to the participant for oral ingestion in the clinic; Bottle 2 (for applicable visits) will be given to participant to take home with instructions to take 1 tablet orally every day for the rest of the week.
	Same as for active treatment

Study Treatment Name	AGN-241751	Placebo
Packaging and Labeling	
Allergan will provide study treatment in the form of identically appearing tablets containing AGN-241751 doses of 3 mg, 10 mg, 25 mg, or placebo.
 
All participants will receive single-blind placebo tablets for Days 2 to 7.
	
Allergan will provide study treatment in the form of identically appearing tablets containing AGN-241751 doses of 3 mg, 10 mg, 25 mg, or placebo.

Manufacturer	Allergan, Inc.	Allergan, Inc.

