4.0 INTRODUCTION

This statistical analysis plan (SAP) provides a more technical and detailed elaboration of the statistical analyses of the efficacy and safety data for part A as outlined and/or specified in the final protocol of Study 3125-104-002 and the most recent protocol amendment (Amendment 1 dated 05 March 2019; Amendment 2 dated 03 May 2019). Specifications of tables, figures, and data listings are contained in a separate document.

Part A of study 3125-104-002 is a Phase 1b, multicenter, randomized, double-blind, placebo-controlled, parallel-group (4 arms), weekly and once daily dose, 2-week study of AGN241751 in participants with major depressive disorder (MDD). The study will include a total of 7 visits and will be approximately 5 weeks in duration:

- Up to 2-week screening period
- 2-week double-blind treatment period
- 1-week safety follow-up period

After providing written consent, participants will enter a screening period of up to 14 days. Screening procedures may be conducted on up to 2 separate dates where necessary to accommodate participant and site schedule; however, every effort should be made to conduct all procedures as early as possible in the screening period, including the rater-administered montgomery- asberg depression rating scale (MADRS). Participants meeting the eligibility criteria at the end of Visit 2 (Day 1 of the randomized inpatient treatment) will be assigned a treatment and enter the double-blind treatment period.

Approximately 100 participants are planned for enrollment in the double-blind treatment period (25 participants each in the AGN-241751 and placebo groups). Participants will be randomized in a ratio of 1:1:1:1 to 1 of 4 treatment groups: 3 mg, 10 mg, and 25 mg dose AGN-241751 and placebo. All participants will be randomized to receive active treatment or placebo (Day 1, and Days 8 to 15) and placebo alone (Days 2 through 7).

[figure not shown]

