AGN-241751 is being developed for once-weekly dosing; however, the impact of repeated administration of AGN-241751 requires testing. In order to minimize participant's expectations and control for placebo response while changing dosing regimens, all treatments will be presented to participants as oral daily dosing throughout the study. On Day 1, all participants will be randomized to receive the first treatment (ie, 4 treatment groups: 3 mg, 10 mg, and 25 mg dose AGN-241751 or placebo), followed by blinded placebo on Days 2 through 7. Starting on Day 8, participants will then start 7 consecutive days of randomized treatment, administered once daily through Day 15.

On Day 1, site staff will give the participant the single dose of double-blind study treatment from Bottle 1 (for applicable visit) to take by oral ingestion in the clinic (ie, the first dose of study treatment for that week). Site staff will then give Bottle 2 (for applicable visits), which contains the single-blind placebo tablets, to the participant with the instruction to take 1 tablet daily by oral ingestion for the remainder of that week (Days 2 through 7). On Day 8, site staff will give the participant the single dose of double-blind study treatment from Bottle 1 (for applicable visit) to take by oral ingestion in the clinic (ie, the first dose of study treatment for that week). Site staff will then give Bottle 2 (for applicable visits), which contains double-blind study treatment, to the participant with the instruction to take 1 tablet daily by oral ingestion for the remainder of that week (Days 9 through 15).

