Participants will have 7 study visits during the study. The first 6 visits will occur in the following pattern: the Screening Visit (Visit 1; up to Day -14); at Visit 2 (Day 1 of the randomized inpatient treatment); at Visit 3 (1 day following the inpatient treatment day); at Visit 4 (7 days following the first inpatient treatment day, which is the second inpatient treatment day); at Visit 5 (1 day following the second inpatient treatment day); and at Visit 6 (7 days following the second inpatient treatment day). If necessary, study visits may be conducted up to 2 days before or after the scheduled visits with the exception of visits that are 1 day apart (ie, Visits 2 and 3 must be conducted 1 day apart; and Visits 4 and 5 must be conducted 1 day apart). Participants will enter a 1-week safety follow-up period and return for Visit 7. Participants who prematurely discontinue from the study before completing the double-blind treatment should enter the 1-week safety follow-up period. Additional follow-up visits may be scheduled within 30 days, if necessary for safety reasons.

Figure 4-1

Study Design Diagram

FU = follow-up; IP = investigational product.

All treatments will be presented to participants as oral once daily dosing throughout the study.

At Visit 2 (Day 1 of the randomized inpatient treatment), all participants will be randomized to receive the first treatment, followed by blinded placebo on Days 2 through 7.

Starting at Visit 4 (Day 8), participants will then start 7 consecutive days of double blinded randomized treatment, administered once daily through Day 15.

The schedule of activities for Study 3125-104-002 is presented in [Table 4-1](#). The double-blind treatment period starts with the first dose of study (Day 1) treatment and ends with the last dosing day (Day 15).

Table 4-1 Schedule of Activities (SoA)							
		Double-blind Treatment Period					Safety Follow-up Period
Visit	Screening (1)	2	3	4	5	6/ET^a	7
Study Day	up to -14 days	1	2	8	9	15	22
Informed consent	x						
Medical (surgical, neurologic) and psychiatric histories	x						
Prior medication history	x						
Inclusion/exclusion	x	x					
Randomization assessment		x					
Clinical laboratory determinations ^b	x	x				x	
Urine drug screen	x					x	
Serum pregnancy test	x					x	
Pharmacogenomics consent and sample ^c				x			
Vital signs ^d	x	x	x	x	x	x	x
ECG	x					x	
Physical examination	x					x	
SCID	x						
MADRS	x	x	x	x	x	x	x
CGI-S	x	x	x	x	x	x	
BPRS+	x		x	x	x	x	
CADSS	x		x	x	x	x	

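### The Part A compliance rate in SAP 9.2 pools six placebo-week tablets with the randomised tablets, so 5 of 8 repeated doses can pass as compliant, and missing 4 or more placebo tablets alone can fail.

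*SAP*

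**What the plan says.** SAP 9.2 plans one percentage per participant for the double-blind treatment period. The fraction behind it reads: "number of tablets actually taken by a participant during that period divided by the number of days the participants are expected to be taken". Numerator and denominator both cover that whole period. The classification follows: "If a participant achieved 80 to 120 percent compliance, then participant is considered as a compliant". Only the number and percentage of compliant participants are then summarised.

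SAP 4.0 fixes the period: "The double-blind treatment period starts with the first dose of study (Day 1) treatment and ends with the last dosing day (Day 15"). The same section sets out what is taken within it: "All participants will be randomized to receive active treatment or placebo (Day 1, and Days 8 to 15) and placebo alone (Days 2 through 7"). The first-week home bottle comes with an "instruction to take 1 tablet daily by oral ingestion for the remainder of that week (Days 2 through 7"), and the second-week bottle with an "instruction to take 1 tablet daily by oral ingestion for the remainder of that week (Days 9 through 15"), after a clinic tablet on Day 8. The treatment table in Protocol 7.1.1 confirms the content of the first-week bottle: "All participants will receive single-blind placebo tablets for Days 2 to 7".

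SAP 9.1 does separate the regimen for another measure: "Treatment duration overall and by treatment regimen intervals (Day 1, Day 2-Day 7, Day 8-Day 15"). SAP 9.2 makes no such split and does not exclude the placebo-week tablets.

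**The concern.** Days 2 to 7 are identical in all four arms. Tablets taken in that week say nothing about whether the randomised treatment was delivered, yet they make up 6/15 = 40% of the compliance denominator. A well-kept placebo week can therefore offset missed doses in the repeated-dose week, and a poor placebo week can mark down a participant who missed no randomised tablet.

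The place where this matters is Day 15, a key secondary time point that tests repeated daily dosing. On the Day 8 to 15 schedule, seven of the eight tablets in that interval are taken at home. If the Day 15 comparison shows little difference, a reader will want to know how fully the repeated regimen was taken, and the pooled rate answers a different question.

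**Working it through.** **Inputs**
- Day 1: 1 randomised tablet in the clinic (SAP 4.0).
- Days 2 to 7: 6 placebo tablets at home (SAP 4.0; Protocol 7.1.1).
- Days 8 to 15: 1 clinic tablet plus 7 home tablets = 8 randomised tablets (SAP 4.0).
- Compliant band: 80 to 120 percent, bounds included (SAP 9.2). Protocol 7.6.1 calls compliance poor only below 80% or above 120%, so exactly 80% passes in both documents.

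The band is a convention, so the plan has no derived figure to reproduce.

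**Formula.** With *p* placebo tablets and *r* repeated-dose tablets taken, and the Day 1 tablet taken:

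Pooled compliance = 100 × (1 + *p* + *r*) / (1 + 6 + 8) = 100 × (1 + *p* + *r*) / 15

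The lower bound is 0.80 × 15 = 12 tablets, so three missed tablets are tolerated wherever they fall.

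**Results on the 15-tablet schedule**

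| Tablets missed | Pooled rate | SAP 9.2 class | Days 8–15 | All randomised |
|---|---|---|---|---|
| 3 repeated-dose | 12/15 = 80.0% | compliant | 5/8 = 62.5% | 6/9 = 66.7% |
| 4 repeated-dose | 11/15 = 73.3% | non-compliant | 4/8 = 50.0% | 5/9 = 55.6% |
| 1 placebo | 14/15 = 93.3% | compliant | 8/8 = 100% | 9/9 = 100% |
| 2 placebo | 13/15 = 86.7% | compliant | 8/8 = 100% | 9/9 = 100% |
| 3 placebo | 12/15 = 80.0% | compliant | 8/8 = 100% | 9/9 = 100% |
| 4 placebo | 11/15 = 73.3% | non-compliant | 8/8 = 100% | 9/9 = 100% |
| 6 placebo | 9/15 = 60.0% | non-compliant | 8/8 = 100% | 9/9 = 100% |

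**Second reading of the schedule.** SAP 4.0 also describes the repeated-dose interval as seven consecutive days from Day 8, while ending it on Day 15. Day 8 to Day 15 is eight days, so the two statements conflict. With 7 tablets the total is 1 + 6 + 7 = 14 and the lower bound is 0.80 × 14 = 11.2, so 12 tablets are needed:
- 5 of 7 repeated-dose tablets (71.4%) pools to 12/14 = 85.7%, compliant.
- 4 of 7 pools to 11/14 = 78.6%, non-compliant.
- All randomised tablets taken, 3 placebo tablets missed: 11/14 = 78.6%, non-compliant.

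**Visit windows.** Visits 4 and 6 may move by 2 days. Assume one tablet a day, with the placebo bottle used until Visit 4 and the second-week bottle through Visit 6. The total then runs from 13 to 17 tablets, and two or three missed tablets are tolerated. The lowest repeated-dose intake still classed compliant ranges from 50.0% (Visit 4 on Day 10 and Visit 6 on Day 13: 4 repeated-dose tablets, 2 missed) to 77.8% (Visit 4 on Day 6 and Visit 6 on Day 14: 9 tablets, 2 missed). The windows change the counts but do not remove the pooling.

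**The case against.** The best defence is that Protocol section 7 counts placebo as study treatment, and every participant is told to take one tablet a day throughout. Missing four of six assigned tablets is real non-compliance with the assigned regimen, and the 80%/120% limits match Protocol 7.6.1. That stands as a reason to keep a pooled figure. It does not make the pooled figure a measure of adherence to the randomised treatment.

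Second, the 5-of-8 case lies exactly on the bound. It requires a perfect placebo week, and one more missed tablet fails. A reader might infer that a whole arm could look adherent after missing more than a third of its repeated doses. That would need essentially every participant to sit on the bound with every placebo tablet taken. On the 14-tablet reading, the most that can be missed is 2/7 = 28.6%. The documents give no reason to expect such a pattern.

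Third, a reader might infer that missing only placebo tablets makes a participant non-compliant. It does so only from four missed tablets (three on the 14-tablet reading).

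Fourth, a reader might take the compliant rate to be the only planned view of delivery. SAP 9.1 also plans exposure statistics for each study day and duration by interval, and SAP 8.0 plans a listing of significant protocol deviations. These help only in part. Duration runs from first to last dose date, so it cannot show tablets skipped in between. The per-day statistics do not state what is measured, and Part A home dosing is checked by counts of returned tablets, which do not show the day a tablet was missed. Part A describes no dosing diary, unlike Part B.

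**Conclusion.** The pooling is in the text, and it can classify participants in the wrong direction as regards randomised treatment. On the 15-tablet schedule, a participant can be compliant with 62.5% of the repeated-dose tablets taken, and non-compliant with 100% of the randomised tablets taken. On the 14-tablet reading, the first figure becomes 71.4%.

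The consequence is limited. Compliance is summarised descriptively, defines neither the mITT nor the safety population, and enters no efficacy model. The Day 2 primary endpoint follows a single tablet given in the clinic. What is affected is interpretation of the Day 15 result, because the compliant rate is the only defined adherence rate. It would go too far to say that a null Day 15 result will be misread as lack of effect, since other exposure summaries are planned. The examples assume nominal visit days and that the Day 1 tablet was taken. This is a cheap improvement, not a threat to the trial's conclusions.

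**What to change.** In SAP 9.2:
- Report compliance separately for Day 1, Days 2 to 7 and Days 8 to 15, the intervals SAP 9.1 uses for duration.
- Apply the 80 to 120 percent classification to the randomised tablets (Day 1 plus Days 8 to 15), and separately to Days 8 to 15 among participants who entered that interval. Classifying on Days 8 to 15 alone would drop the dose behind the primary endpoint and leave those who stopped earlier without a denominator.
- Keep the pooled figure as a secondary line.
- Reconcile the seven-consecutive-days wording with the Day 15 end of dosing, so that the denominator is fixed.

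The change concerns reporting only and leaves dosing and the investigator's compliance review in Protocol 7.6.1 as they are. The cost is a few lines of SAP text and a little more programming. Interval counts should be available, because Protocol 7.6.1 asks sites to collect unused tablets before dispensing more, and the schedule lists compliance checks at Visits 4, 5 and 6. The reported compliant rate may be slightly lower.
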